5.4 End of Treatment

Safety Run-In and Randomized Treatment:

The End of Treatment (EOT) visit, Day 337 (or sooner if the patient discontinues active treatment) is the last dose of nivolumab and the last dose of Troriluzole vs. placebo. EOT assessments are listed in Section 10 (Study Calendar).

Participants removed from active protocol therapy for unacceptable adverse event(s) will receive management and supportive care for the adverse event until resolution or stabilization of the adverse event, per the treating investigator. During this time, participants must present for in-person visits at least every 12 weeks \pm 1 week.

Following EOT, participants may continue on nivolumab therapy indefinitely, as it is FDA approved without a maximum duration. Continuation of nivolumab is not required for this protocol. Patients who have completed the last dose of study medication (Day 337) should discuss their individual treatment plans with their treating physician. See Section 5.9 for protocol-required follow up.

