5.9 Duration of Follow Up

Safety Run-In and Randomized Treatment:

Participants will be followed with in-person visits on Days 421, 505, and 589, or until death, whichever occurs first. If they are receiving additional nivolumab, this should be documented in the progress notes and reported in the case report forms. Treatment-emergent AEs should continue to be monitored during the follow-up period (until resolution). New AEs during follow up that are not related to treatment should not be recorded.

Tumor assessments will be performed as per standard of care during Days 421-589 and will be captured on CRFs.

Day 673 is the last required in-person visit. Subjects will continue to be contacted (or their charts will be accessed) for information on subsequent therapy and vital status for a total of 3 years. The study team will contact participants by phone every 12 weeks (+/- 14 days) to assess survival.

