	Baseline	Cycles 1-4: Induction				Cycles 5-13			End of Treatment (EOT) Cycle 14	Follow-Up Visit #1	Follow-Up Visits #2-4 ⁱ	Final Follow-Up Visit ^j	EDC Timepoints
		Day 1	Day 22	Day 43	Day 64	Day: 85 169 253	Day: 113 197 281	Day: 141 225 309	Day 337 or sooner	Within 30 days post EOT	Day: 421 505 589	Day 673 or sooner	
cranial tumor measurements ^d													during any other Cycle, it must be captured in EDC.
CT CAP (or PET/CT) for extra-cranial tumor measurements ^e	X					X			X				Baseline, Day 85, 169, 253. If Extracranial Tumor Measurements are performed during any other Cycle, it must be captured in EDC.
Research blood samples ^f	X			X		X			X				N/A
Archival tumor specimen (6-10 unstained slides)	X												N/A
Research fresh tumor biopsy and additional blood draw (optional) ^g	X			X									N/A
Concurrent Medications		X-----X										Final Follow-Up Visit (Steroid use only)	
Adverse Event Evaluation		X-----X										All visits.	

	Baseline	Cycles 1-4: Induction				Cycles 5-13			End of Treatment (EOT) Cycle 14	Follow-Up Visit #1	Follow-Up Visits #2-4 ⁱ	Final Follow-Up Visit ^j	EDC Timepoints
		Day 1	Day 22	Day 43	Day 64	Day: 85 169 253	Day: 113 197 281	Day: 141 225 309	Day 337 or sooner	Within 30 days post EOT	Day: 421 505 589	Day 673 or sooner	
Other correlative studies on tumor tissue – if brain surgery occurs during the study period^h		X-----X										If brain surgery is performed, EDC should capture date, and which tumor was removed.	
Concurrent radiation therapy		X-----X										If brain or body RT is performed, EDC should capture start/end dates, # fractions, and total dose (cGy) to each tumor that was irradiated.	
Survival		X-----X										N/A	

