
g: Fresh biopsy of extracranial disease (optional). The second biopsy may occur at any time between Days 43 and 64 to facilitate scheduling. Patients will also have 2 CPT top tubes (10 mL tubes) drawn on the day of the fresh tumor biopsies. Biopsy and shipping must occur Monday – Thursday.
 
h: If patient is having a craniotomy per standard of care, tumor sample from brain metastasis and 1-2 green top vials of CSF will be collected when feasible.
 
i: Follow-up visits #2-4. If patients discontinue treatment early, they should be evaluated in-person every 84 days (or more frequently as indicated) until 5 Follow-Up visits have been completed.
 
j: Final In-Person visit. Survival data will continue to be collected for 3 years, unless patient dies or withdraws consent to be followed. The study team will contact participants by phone every 12 weeks (+/- 14 days) to assess survival.
													

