11. MEASUREMENT OF EFFECT

11.1 Antitumor Effect – Intracranial tumors and Extracranial tumors

Assessment of extracranial disease (by CT scan or other approved modalities) and intracranial disease (by MRI scan with a minimum of 3 mm cuts) will be performed per the schedule in Section 10, Study Calendar.

Investigators may obtain more frequent scans as medically indicated.

Response and progression will be evaluated in this study using the international criteria proposed by the Response Evaluation Criteria in Solid Tumors (RECIST) guideline (version 1.1)³⁹ for all extracranial lesions and modified RECIST 1.1 for all brain lesions (see Section 11.3).

Changes in the largest diameter (unidimensional measurement) of the tumor lesions and the shortest diameter in the case of malignant lymph nodes are used in the RECIST criteria.

Definitions

Evaluable for Target Disease response. Only those participants who have measurable disease present at baseline, have received at least one cycle of therapy, and have had their disease re-evaluated will be considered evaluable for target disease response. These participants will have their response classified according to the definitions stated below. (Note: Participants who exhibit objective disease progression prior to the end of cycle 1 will also be considered evaluable.)

Evaluable Non-Target Disease Response. Participants who have lesions present at baseline that are evaluable but do not meet the definitions of measurable disease, have received at least one cycle (3 weeks) of therapy, and have had their disease re-evaluated will be considered evaluable for non-target disease. The response assessment is based on the presence, absence, or unequivocal progression of the lesions.

Disease Parameters

Measurable disease, intracranial (brain lesions). Measurable brain lesions are defined in this study as those that can be accurately **measured in at least one dimension (longest diameter to be recorded) as ≥ 5 mm with MRI**. All tumor measurements must be recorded in millimeters (or decimal fractions of centimeters).

Note: Brain metastases that have previously been treated with radiation therapy are not considered measurable, unless they have grown and the treating investigator considers them to be refractory to radiation.

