Although a clear progression of “non-target” lesions only is exceptional, the opinion of the treating physician should prevail in such circumstances, and the progression status should be confirmed at a later time by the review panel (or Principal Investigator).

Evaluation of New Lesions

The finding of a new lesion should be unequivocal (i.e. not due to difference in scanning technique, imaging modality, or findings thought to represent something other than tumor (for example, some ‘new’ bone lesions may be simply healing or

flare of pre-existing lesions). However, a lesion identified on a follow-up scan in an anatomical location that was not scanned at baseline is considered new and will indicate PD. If a new lesion is equivocal (because of small size etc.), follow-up evaluation will clarify if it truly represents new disease and if PD is confirmed, progression should be declared using the date of the initial scan on which the lesion was discovered.

Evaluation of Best Overall Response

The best overall response is the best response recorded from the start of the treatment until disease progression/recurrence (taking as reference for progressive disease the smallest measurements recorded since the treatment started). The patient's best response assignment will depend on the achievement of both measurement and confirmation criteria.

Evaluation of BOR

Target Lesions	Non-Target Lesions	New Lesions*	Overall Response
CR	CR	No	CR
CR	Non-CR/Non-PD	No	PR
CR	Not evaluated	No	PR
PR	Non-CR/Non-PD/not evaluated	No	PR
SD	Non-CR/Non-PD/not evaluated	No	SD
PD	Any	Yes or No	PD
Any	PD**	Yes or No	PD
Any	Any	Yes	PD

* See RECIST 1.1 manuscript for further details on what is evidence of a new lesion.

** In exceptional circumstances, unequivocal progression in non-target lesions may be accepted as disease progression.

Note: Participants with a global deterioration of health status requiring discontinuation of treatment without objective evidence of disease progression at that time should be reported as “*symptomatic deterioration.*” Every effort should be made to document the objective progression even after discontinuation of treatment.

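### Patients who stop all protocol agents before Day 169 without progression need no MRI or CT before 6 months, and the two primary-PFS censoring rules treat them differently

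*Combined protocol and SAP*

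**What the plan says.** The Study Calendar (Section 10) places brain MRI at baseline, Days 43, 85, 169 and 253, and EOT. CT follows the same schedule without Day 43. The scan rows are empty in every follow-up column. Section 11.1 ties disease assessment to this calendar.

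Section 5.4 sets EOT at Day 337, "or sooner if the patient discontinues active treatment", and defines it as the last dose of nivolumab and of troriluzole/placebo. After an early EOT, calendar footnote i says: "If patients discontinue treatment early, they should be evaluated in-person every 84 days". For patients stopped for adverse events, 5.4 adds that "participants must present for in-person visits at least every 12 weeks". Neither sentence mentions imaging.

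The only imaging text after EOT is in 5.9, repeated in footnote e: "Tumor assessments will be performed as per standard of care during Days 421-589". Later contacts are "for information on subsequent therapy and vital status for a total of 3 years", which does not include progression.

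The primary endpoint is global PFS, with particular interest in 6 months, analysed by intention to treat (13.1, 13.7). For patients alive without progression, 11.5 censors at the last disease evaluation and 13.1 at the last follow-up visit. For intracranial and extracranial PFS, 13.6 uses the last adequate disease assessment.

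**The concern.** Six months is about Day 183, so Day 169 is the last scheduled scan before the time point of interest. A patient who ends all treatment earlier without progression is seen in clinic but need not be scanned. Silent progression, which is plausible in small asymptomatic brain metastases, can then go unrecorded.

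The censoring rule decides the consequence. Under 11.5 the patient leaves the risk set at the EOT scan and information is lost. Under 13.1 the patient counts as progression-free through visits at which nobody looked, and PFS is overstated. If such stops are more frequent in one arm, the overstatement differs by arm. That is possible here, because 6.7 lists toxicities shared by all three drugs. Scans that were never done cannot be recovered at analysis.

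**Working it through.** **1. Tracing one patient.** Section 6.6 says immune-related events commonly start 3 to 10 weeks from first dose. Take EOT on Day 71 (week 10). The five follow-up visits in footnote i fall at about Day 101 (within 30 days), then every 84 days: Days 185, 269, 353 and 437. None requires a scan. A patient first held at week 3 or week 10 for the 12-week maximum stops at about Day 106 or Day 155, still before Day 169.

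**2. The plan's own model (13.2).** Inputs: INP 6-month PFS 0.60, taken as the whole-arm value; cured 30% (INP) and 50% (INT); hazard ratio 0.557. With S(t) = p + (1 − p)exp(−ht), t in months:
- INP: h = ln(0.70/0.30)/6 = 0.1412.
- INT: h = 0.557 × 0.1412 = 0.0787, so S(6) = 0.5 + 0.5 × exp(−0.472) = 0.812.

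This agrees with the plan's figure of approximately 0.8. The planned difference is 0.212.

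**3. Number affected, upper range.** Section 2.5 cites toxicity discontinuation of 27% and 36%: 0.27 × 90 = 24 and 0.36 × 90 = 32 patients. These rates describe ipilimumab/nivolumab and come without timing.

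**4. Reading under 13.1.** Assumptions: a fraction f stops all agents at a time uniform over months 1 to 4, equally in both arms; 20% of first PFS events are deaths, which are still captured; no standard-of-care scans are done.

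Overstatement at 6 months = f × 0.8 × [mean S(u) − S(6)], where mean S(u) = p + (1 − p)(e^(−h) − e^(−4h))/(3h).
- INP: mean S(u) = 0.3 + 0.7 × 0.7078 = 0.7955; gap 0.1955.
- INT: mean S(u) = 0.5 + 0.5 × 0.8234 = 0.9117; gap 0.0998.

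| f | INP reads | INT reads | Difference |
|---|---|---|---|
| 27% | 0.600 + 0.042 = 0.642 | 0.812 + 0.022 = 0.833 | 0.191 |
| 36% | 0.600 + 0.056 = 0.656 | 0.812 + 0.029 = 0.841 | 0.184 |

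Simulation under the same assumptions gives 0.643/0.832 and 0.656/0.840, differences of 0.189 and 0.184. If standard-of-care scans catch half of the hidden progressions, simulation gives 0.619/0.822 and 0.630/0.826, differences of 0.203 and 0.196. At a 10% stop rate with no such scans it gives 0.617/0.819.

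**5. No true effect, unequal stopping.** Both arms have 30% cured and the same hazard, with 45 patients per arm and a log-rank test standing in for the planned mixture-cure test. With 27% stopping on INP and 36% on INT, one-sided rejection in favour of INT under 13.1 is 15.2% against a nominal 10% (3,000 runs). A two-sided 10% test rejects 11.4% of the time. Section 13.2 does not state sidedness. Under 11.5 the one-sided figure is 9.5%.

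**6. Reading under 11.5.** PFS at 6 months stays at about 0.60 and 0.81 if censoring is unrelated to outcome. Expected events fall from 48.5 to 40.8 (27%) or 38.4 (36%).

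**The case against.** **Most toxicity stops may not reach EOT.** Checkpoint stops in 6.4 are agent-specific. Under 6.3 troriluzole continues through an interruption of the antibodies for an unrelated event, and the antibodies may continue when troriluzole is held or stopped. Patients who keep either stay on the calendar. This stands: the point covers only patients who stop everything, and 27% to 36% is a ceiling. A reader might infer that every toxicity stop goes unscanned; the documents do not support that.

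**Scans will happen anyway.** Section 11.1 says "Investigators may obtain more frequent scans as medically indicated", and the calendar's data-capture column says "If Extracranial Tumor Measurements are performed during any other Cycle, it must be captured in EDC". The first is a permission and the second records scans that are done; neither requires one. The sentence "Every effort should be made to document the objective progression even after discontinuation of treatment" belongs to the note on symptomatic deterioration. Routine imaging would shrink the effect, which is why the half-caught case is shown.

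**The standard-of-care capture may move with the visits.** Days 421 to 589 are follow-up visits 2 to 4, which footnote i re-times for early stoppers. On that reading the Day 71 patient has an assessment captured near Day 185. This is a fair reading, but still not a mandated scan.

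**Scan days could be fixed whatever the treatment status.** This is possible but weak. The columns for Days 85, 169 and 253 are headed as treatment cycles, and footnote i moves early stoppers to the follow-up visits.

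**Section 6.3 might seem to end scanning.** It removes from the study a patient who cannot resume troriluzole within 6 weeks. A reader might infer that assessments stop. Section 5.10 lists only loss to follow-up, withdrawal of consent and death as off-study reasons, so this is a conflict of wording and not an established consequence.

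**Conclusion.** The gap is real but narrow: no scan is mandated between an early EOT that ends all agents and 6 months. Section 13.1 is the outlier among the censoring rules and is wrong as written, because it credits unscanned time as progression-free.

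The sizes in steps 4 and 5 rest on assumed stop timing, captured deaths and the upper-range stop rates. With equal stopping, the 13.1 rule narrows the arm difference by about 2 to 3 points, or 1 to 2 if half of the hidden progressions are found. It favours INT falsely only if stops are more frequent there; the 36% used for INT is an illustration, not a forecast. Under 11.5 there is no bias if censoring is non-informative, only lost precision. That condition is not assured, since deaths after the EOT scan still count while silent progressions are lost.

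Two stronger readings go too far. A reader might put every stop on Day 71 among progression-free patients with no deaths captured, which would take INP to 0.67 or 0.69; nothing in the documents supports that timing. A reader might also infer a definite loss of power. The plan fixes neither the stop rate nor the frequency of routine scans, and the log-rank test used here is only a proxy for the planned one, so none is claimed.

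**What to change.** 1. **Section 13.1:** censor primary PFS at the last adequate disease assessment, in line with 11.5 and 13.6. This corrects a stated rule at no cost.
2. **Calendar footnotes d, e and i:** state that MRI and CT continue on the calendar days counted from Day 1 (MRI on Day 43; both on Days 85, 169, 253 and 337) until progression, death or withdrawal of consent, whichever agents have stopped. Day 337 matches the EOT scan that completers receive. A patient stopping on Day 71 would need four pairs, so the ceiling is about 4 × 24 = 96 to 4 × 32 = 128 MRI/CT pairs, plus a Day 43 MRI for anyone stopping before then. The actual number should be lower, because some patients keep an agent or progress first, and many of the scans would be standard of care. The downside is scan burden for patients already off treatment.
3. **Section 6.3:** replace removal from the study with wording that the patient is taken off troriluzole/placebo and study assessments continue, consistent with 5.10. No cost.

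Item 1 removes the false credit but leaves early censoring, so item 2 is needed to recover the information. The sample size does not change. Clarifying in 5.4, 5.8 and Table 6.1 which agents an adverse event stops would help but is optional.

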Following the Safety Run-in, all participants will be enrolled on the randomized portion of the study.

Primary Endpoint. The primary endpoint of the study is global progression-free survival in patients with melanoma brain metastases who are treated with INT vs. INP. Of particular interest will be PFS at 6 months.

PFS is defined as the time from random assignment to the earlier of death or documented disease progression in the intracranial or extracranial compartments. The follow-up of patients who have neither died nor progressed will be censored at the date of the last follow-up visit.

Secondary Endpoints. The secondary objectives and their associated endpoints evaluate other important clinical outcomes, including overall survival (OS), intracranial response rate (RR) and

PFS, extracranial RR and PFS, and safety (number of participants experiencing adverse events, particularly neurologic events). We will also investigate:

- tolerability (number of induction cycles administered, number of maintenance cycles administered)
- use of corticosteroids for management of symptomatic cerebral edema (number of participants)
- use of corticosteroids for management of immune related adverse events (number of participants who require prednisone ≥ 1 mg/kg or equivalent)
- frequency of clinically-indicated stereotactic radiation therapy to the brain on study (number of patients, number of instances and number of lesions irradiated)
- frequency of clinically-indicated surgical intervention to the brain on study (number of participants)

Planned subgroup analyses according to baseline characteristics:

- Prior anti-PD-1 exposure (yes vs. no – if yes then adjuvant vs. metastatic setting)
- Prior ipilimumab exposure (yes vs. no)
- Age (<65 years vs 65 years or older)
- ECOG (0 vs 1)
- LDH at baseline (normal vs. elevated)
- Number of brain metastases (<3 vs 3 or more)
- Brain-directed stereotactic radiation therapy prior to study entry (yes vs. no)
- Craniotomy prior to study entry (yes vs. no)

Planned subgroup analyses according to on-study events:

- On-study brain-directed stereotactic radiation therapy (yes vs. no)

Exploratory Endpoints:

- associations between BRAF/NRAS mutation status and response endpoints, as well as tissue biomarker profiles between paired tissues from extracranial and intracranial metastases from individual patients, where available

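### Section 5.9 and calendar footnote i give early stoppers different in-person follow-up; if the footnote governs, on-study counts of steroid use, and possibly SRT and brain surgery, rest on windows that depend on when treatment stops

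*Combined protocol and SAP*

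**What the plan says.** Section 5.9, headed for both the safety run-in and the randomized part, states: "Participants will be followed with in-person visits on Days 421, 505, and 589, or until death, whichever occurs first". It adds that "Day 673 is the last required in-person visit". Patients who stop early are not mentioned.

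The Section 10 calendar treats them separately. Footnote i, attached to Follow-Up Visits #2-4, says that "they should be evaluated in-person every 84 days (or more frequently as indicated) until 5 Follow-Up visits have been completed". The five are Visit #1 ("Within 30 days post EOT"), Visits #2-4 and the Final visit, whose column is headed "Day 673 or sooner". Section 5.4 also lets the starting point move: "The End of Treatment (EOT) visit, Day 337 (or sooner if the patient discontinues active treatment").

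Sections 1.3 and 13.1 list steroid use, brain SRT and brain surgery as secondary endpoints in the form of counts, for example "frequency of clinically-indicated surgical intervention to the brain on study (number of participants"). SRT is also counted by instances and by lesions. The documents do not define when a patient is on study for these counts. Section 13.6 gives them no analysis method, common window or person-time denominator. Its landmark approach covers the radiation-salvage and steroid-treated subgroups only.

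Three other rules bear on what is captured:
- The calendar's data-entry column runs concurrent-medication capture, for steroid use only, to the Final Follow-Up Visit.
- Section 5.9 continues phone or chart contact for subsequent therapy and vital status for 3 years.
- Section 7.3 ties adverse event reporting to 30 days after the last dose.

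**The concern.** A site with an early stopper cannot tell which rule applies. Under Section 5.9 the patient is seen to Day 673. Under footnote i in-person visits end after the fifth, wherever that falls.

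If footnote i governs, the length of in-person observation grows day for day with time on drug. Time on drug is a post-randomization outcome, and the trial is designed on the hypothesis that it differs by arm. A count with no common window then mixes how often an event happens with how long the patient was watched. At stake is the reading of the secondary endpoints on steroid use, SRT and brain surgery. The primary PFS analysis is not at issue here, and neither is survival follow-up, which runs for 3 years by phone or chart.

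**Working it through.** **1. Reproduce the plan's figure.** Planned end of treatment is Day 337 (Section 5.4) and the later visits are 84 days apart: 337 + 4 × 84 = 673. This matches Section 5.9 exactly, so footnote i and Section 5.9 coincide for completers, with 673 − 337 = 336 days of follow-up.

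**2. Apply footnote i to early stoppers.** Last in-person visit = stop day + 336.

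| Stop day | Last visit | Short of Day 673 by |
|---|---|---|
| 22 | 358 | 315 days |
| 64 | 400 | 273 days |
| 85 | 421 | 252 days |
| 169 | 505 | 168 days |
| 253 | 589 | 84 days |
| 337 | 673 | 0 |

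A Day 64 stopper has 400/673 = 59% of the full window and finishes before Section 5.9's first fixed visit on Day 421. Other readings of the footnote give 366 days (first visit at 30 days, then 4 × 84) or 420 days (5 × 84). A Day 64 stopper then ends on Day 430 or 484, still well short of Day 673.

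**3. Mean window by arm if footnote i governs.** Inputs from Section 13.2: 6-month PFS of 0.6 on INP, 30% and 50% cured, hazard ratio 0.557. Assumed: treatment ends at progression or Day 337, no deaths, 30.44 days per month.

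- INP rate: 0.3 + 0.7·exp(−6λ) = 0.6, so λ = 0.1412 per month. INT rate: 0.557 × 0.1412 = 0.0787 per month. Check: 0.5 + 0.5·exp(−6 × 0.0787) = 0.81, in line with the plan's figure of about 0.8.
- Mean time on treatment = c·337 + (1 − c)·[1 − exp(−337λ)]/λ, with c the cured fraction and λ per day.
- INP: 0.3 × 337 + 0.7 × 170.4 = 220 days. INT: 0.5 × 337 + 0.5 × 225.0 = 281 days.
- Adding 336 days: **556 days on INP and 617 on INT**, a gap of 61 days (11%).
- Adding toxicity stops in 27% to 36% of patients (the discontinuation rates quoted in Sections 2.5), with timing assumed uniform over Days 22-113: 499-513 against 539-559 days (8-9%).

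**4. Effect on a count.** Assume the same constant event rate in both arms, with 20% risk at 12 months (an assumption; the documents give none). P(at least one event) = 1 − exp(−rate × window), with rate = −ln(0.8)/365 per day. This gives 28.8% at 556 days and 31.4% at 617 days. With about 45 patients per arm (up to 90 randomized), the difference is 45 × 0.026 = 1.2 patients. At 10% and 30% risk it is 0.7 and 1.5 patients. With the toxicity stops and 20% risk it is 0.8 to 0.9.

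**5. Does the net count rise with time on drug?** Not necessarily. Expected events are equal in a Day 64 stopper and a completer when the stopper's rate is 673/400 = 1.7 times higher; for a Day 169 stopper it is 673/505 = 1.3 times. Above those ratios the early stopper contributes more events despite the shorter window. On the Section 13.2 assumptions, progression by Day 337 is 0.7 × (1 − e^−1.56) = 55% on INP and 0.5 × (1 − e^−0.87) = 29% on INT, so events triggered by progression could well be fewer on INT.

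**The case against.** The strongest defence is that there is no contradiction. Section 5.9 describes the completer, footnote i is the specific rule for early stoppers, and the calendar heading "Day 673 or sooner" fits that reading. This is plausible, and "for everyone" is only inferred from Section 5.9's silence. But Section 5.9 does not refer to the footnote, and Section 5.10 does not list completing five visits as a way of leaving the study. If the footnote is the exception, the unequal window is real; if Section 5.9 governs, it disappears. Either way the text has to say so.

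A reader might infer that INT must collect more SRT, surgery and steroid courses simply because it is watched longer. The documents do not support that. Sections 5.6 and 5.7 tie on-study SRT and craniotomy to brain progression and limit each to a single episode, and the extra INT time is time without progression. Net counts may be lower on INT.

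A reader might also extend the point to adverse events. That does not hold either: Section 7.3 limits reporting mainly to 30 days after the last dose, Section 5.9 excludes new unrelated events in follow-up, and both apply whichever visit rule governs.

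Nor does footnote i leave survival contact alone. The 3-year follow-up of subsequent therapy may recover SRT and surgery. It does not mention steroid courses.

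Two further points reduce the weight. Section 6.6 says that immune-related events commonly start within 3 to 10 weeks, so first steroid use for them falls mostly in time that nearly all patients share. And Section 13.6 plans no formal between-arm test of these counts. Both limit the size of the problem, but neither supplies a common window.

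**Conclusion.** The point holds in limited form. Section 5.9 and footnote i differ for every patient who stops before Day 337 and must be reconciled. If footnote i governs, early stoppers have a shorter in-person window than completers, and raw counts understate their late events relative to a common window. This is firmest for steroid use, whose capture ends at the Final Follow-Up Visit. For SRT and brain surgery it is possible, unless the 3-year chart follow-up is used to capture them.

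The size is modest: a mean difference of about 61 days between arms under Section 13.2, and roughly one patient in 45 at an assumed 20% yearly risk. Those figures ignore deaths and also ignore treatment continued beyond progression after SRT, which Section 5.8 allows. The bias lies in the opportunity to be counted; the direction of the net arm difference cannot be predicted from the documents.

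**What to change.** 1. Reconcile Section 5.9 and footnote i, with a cross-reference, so that the observation window does not depend on when treatment stops.
2. Define the on-study period for the SRT, surgery and steroid endpoints, and state whether the 3-year follow-up of subsequent therapy feeds the SRT and surgery counts.
3. In Section 13.6, report brain SRT, brain surgery and steroid use by arm over one common window from randomization, as cumulative incidence with death as a competing event, alongside the raw counts. The window can run to Day 673 if Section 5.9 governs. If footnote i governs, it can run to about Day 337, which even a patient stopping on Day 1 reaches (1 + 336 = 337) if alive.

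The cost is calendar and analysis wording and a little more analysis work. The Day 673 window needs about three more visits per early stopper than footnote i, though Section 5.9 already implies them, and some visits after progression will be missed. The Day 337 window needs no extra visits but gives up later events.
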